#### **4.5.2.8 3-Week Trial Stim ON/End of Trial Stage (Visit 5)**

At the end of the 3-week trial stimulation regimen (6-week total SPR Trial Stage), subjects will return for evaluation of primary and secondary endpoints including the BPI, Pain Free Passive Range of Motion, SF-36v2, BDI-II, and the Patient Global Impression of Change scale. The SULCS and QST testing (optional) will

be administered to subjects for which baseline SULCS and QST data are available. Questions regarding general satisfaction and device performance will be asked in the SPR Trial Stage Subject Satisfaction Survey. Subjects will also be queried for medication usage and adverse events. To assess participant compliance with the stimulation regimen, [REDACTED] [REDACTED] will be recorded in the subject records.

The Lead will then be removed during this visit [REDACTED] [REDACTED] The Investigator will perform a visual inspection of the removed Lead. If results of the visual inspection are suggestive of a broken Lead or retained fragment, the Investigators will determine what is medically required to further evaluate and treat the retained fragment.

If the subject achieves a satisfactory response to trial stimulation by demonstrating at least a 2-point reduction in the BPI3 from the End of the Trial Stage stimulation (Visit 5) compared to the End of Sham (Visit 4), the subject will be considered a Trial Stage success. The subject will be followed for up to 6 months to assess the return of pain as described in Section 4.5.2.10. Subjects who demonstrated a negative placebo effect (as evidenced by a worsening of the BPI during the Sham stimulation period) will be compared against Baseline (rather than End of Sham) to assess if they are Trial Stage Successes. Subjects who do not achieve at least a 2-point reduction in BPI will be considered SPR Trial Stage failures.

#### **4.5.2.9 Trial Stage Follow-up Visit (Visit Post-5)**

All subjects will be asked to return to the clinic for a final visit one week following removal of the Lead. During the 1-week follow-up visit, the percutaneous site will be inspected to ensure that there are no signs of infection or other adverse events. SPR Trial Stage failure subjects, and those who choose not to continue, will then be terminated from the study. The Trial Stage Follow-up Calls will be scheduled for all subjects continuing in the protocol. Any AEs noted at this visit will be followed to resolution prior to subject termination.

#### **4.5.2.10 Trial Stage Follow-up Calls (Telephone Calls #a-z)**

Subjects meeting the specified success criteria at Visit 5 will receive monthly phone calls from the study staff until the specified return of pain is reported (for up to 6 months). A return of pain is an increase in the BPI Question #3 score (worst pain in the last week) by at least 2 points and equaling at least a 4 on the scale. In addition to querying the subject about his/her pain, the study staff will also assess for adverse events.

Once a return of pain is reported, an additional call will be scheduled for one week later. During this call, if the subject still reports the specified return of pain, the eligibility visit for the Implant Stage will be scheduled (Visit Pre-6). If the subject no longer reports the specified return of pain, additional phone calls may be conducted until a return of pain is sustained for at least two weeks. At any

time during the six months following Visit 5, Trial Stage Follow-up Calls may be conducted to assess pain. In addition to the monthly calls, the subject may call the study staff at any time within 6 months of Visit 5 to report a return of pain and be assessed for potential eligibility for the Implant Stage. Such a call will be assigned the next call identifier (a through z) and conducted identical to the monthly calls.

If a subject does not report the specified return of pain within 6 months, he/she will be dispositioned as “complete” (see Table 4) and terminated from the study.

During the Trial Stage Follow-up Period, subjects will be permitted to continue use of non-opioid analgesic medications; however, dosages of these medications will be controlled as they are during the Trial Stage and Implant Stage. Subjects will be permitted to reduce or maintain their dosage of non-opioid analgesic medications; however, they will be asked to not increase their dosage of these medications above their baseline dosage at any time (as the phone calls to determine return of pain can occur at any time during the six month period). Subjects will not be permitted to take opioid analgesic medications; receive injections to the affected limb; receive physical or occupational therapy; or, use slings or other stabilization devices/methods during this period.

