## 4.0 STUDY DESIGN

### 4.1 Overview

This study is a prospective non-randomized multicenter case series pilot study to gather preliminary data on the safety, clinical efficacy, and performance of the SPR System for the treatment of post-stroke shoulder pain.

Subjects with chronic ( $\geq 6$  months) post-stroke shoulder pain rated as  $\geq 4$  on the Brief Pain Inventory pain intensity question #3 (BPI3) will receive the first stage of the SPR System. The SPR System is a two-staged neurostimulation therapy which delivers stimulation [REDACTED]. The first stage (SPR Trial Stage) uses a temporary [REDACTED] lead placed percutaneously in [REDACTED] and connected to a body-worn external stimulator (the Smartpatch Stimulator). Subjects meeting the specified success criteria at the conclusion of the SPR Trial Stage who then experience a return of pain within 6 months that is sustained for two consecutive weeks will be consented and screened for eligibility for the second stage (SPR Implant Stage). A “return of pain” is defined as: 1) an increase in pain by at least 2 points compared to the end

of Trial Stage (Visit 5) pain score; and 2) BPI Question #3 score of at least 4 (both criteria must be met for at least 2 weeks). The SPR Implant Stage uses an Implantable Pulse Generator (IPG) and Implantable [REDACTED] Lead.

Subjects will be permitted to continue use of non-opioid analgesic medications throughout the study; however, dosages of these medications will be controlled during the study. Subjects will be permitted to reduce or maintain their dosage of non-opioid analgesic medications, however, they will be asked to not increase their dosage of these medications above their baseline dosage during the week prior to each study visit and scheduled telephone call (and during the Trial Stage follow-up period). Subjects will not be permitted to use opioid analgesic medications (except in the week immediately following the implant stage surgery as needed to control post-surgical pain), or other treatment methods, including slings or other stabilization devices/methods, Botox or steroid injections to the affected shoulder area, etc, during study participation. For this study, Tramadol (Ultram, Ultram ER, or Ultracet) will be considered an opioid medication, and thus, not permitted during study participation. Subjects who require concurrent physical or occupational therapy for shoulder pain will be excluded.

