#### **4.5.3 SPR Implant Stage**

##### **4.5.3.1 Implant Stage Eligibility (Visit Pre-6)**

After a sustained return of pain has been identified, the subject will report to the clinic for Visit Pre-6. First, the study staff will verify that the subject meets all general inclusion and exclusion criteria (with the necessary pain score already having been confirmed at a Trial Stage Follow-up Call). Subjects meeting all general eligibility criteria will be asked if they are interested in participating in the Implant Stage of the study. The Implant Stage Informed Consent Form will be reviewed with the subject to ensure that the risks and benefits of study participation in the Implant Stage are fully understood. The Implant Stage Informed Consent Form may be signed up to 30 days prior to the Implant Stage procedure.

Subjects will then be screened for their cognitive ability to participate in the study and complete the required surveys. The Mini-Mental Status Exam (MMSE) will be administered to determine the subject's continued cognitive ability to participate in the study.

During this visit, the SULCS, and QST testing (optional) will also be administered to subjects for which baseline SULCS and QST data are available.

As a safety precaution to prevent potential excessive bleeding, subjects on warfarin will have blood drawn to confirm an INR of <3.0. If the INR is not below 3.0, subjects will be given the opportunity to have their warfarin dosage adjusted and the INR will be retested up to two additional times. The INR must be collected within 48 hours prior to the Implant Stage procedure. In addition, a pregnancy test will be conducted in females of reproductive potential.

If the subject is determined to be eligible, the Implant Stage procedure (Visit 6) will be scheduled.

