#### **5.4.1.3 Determination of return of pain after Trial Stage**

To determine if a subject is eligible to advance from the SPR Trial Stage to the SPR Implant Stage, the BPI3 will be collected at least monthly for up to 6 months following Visit 5 (the end of Trial Stage stimulation) for those subjects who are Trial Stage successes. For each subject, the BPI3 score reported at the phone call will be compared to the BPI3 score reported at the End of Trial Stim (Visit 5).

If

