**P2=BPI pain score at End of Trial Stim**

**P3=BPI pain score at phone call**

Then, subjects will be eligible to be screened for the Implant Stage if they demonstrate a sustained 2-point or greater increase in their BPI3 score from End of Trial Stim and their new BPI3 score is at least a 4:

$$P_3 - P_2 \geq 2 \text{ (sustained for two consecutive weeks)}$$
$$P_3 \geq 4 \text{ (sustained for two consecutive weeks)}$$

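### Implant Stage success is scored only against Visit 4 or Visit 1, while return of pain is judged against one selected Visit 5 score with repeat calls, so persisting Trial Stage relief can count as implant success.

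*Combined protocol and SAP*

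**What the plan says.** Notation follows the protocol: P0 is BPI3 at baseline (Visit 1), P1 at end of sham (Visit 4), P2 at end of trial stimulation (Visit 5), P3 at a follow-up call and P4 at 12 weeks of IPG stimulation (Visit 10).

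- **Who is followed.** Only Trial Stage successes receive follow-up calls: P2 at least 2 points below the lower of P0 and P1, or zero (Sections 4.1, 4.5.2.10 and 5.4.1).
- **Return of pain.** Section 5.4.1.3 asks for a "sustained 2-point or greater increase in their BPI3 score from End of Trial Stim" together with P3 of at least 4. Section 4.1 adds that "both criteria must be met for at least 2 weeks".
- **Calls.** Section 4.5.2.10 schedules monthly calls for up to 6 months. "Once a return of pain is reported, an additional call will be scheduled for one week later". If that call is negative, "additional phone calls may be conducted until a return of pain is sustained for at least two weeks". Subjects may also call in themselves at any time in the 6 months.
- **Before implant.** Section 4.5.3.1 verifies eligibility at Visit Pre-6 "with the necessary pain score already having been confirmed at a Trial Stage Follow-up Call", and its text names no BPI at that visit. Table 6 has a BPI Short Form row within the eligibility block, but its marks are lost in this copy.
- **Implant Stage success.** Sections 4.1, 5.4.1.4 and 6.1.2.3 and Table 9 compare P4 with P1, or with P0 if pain rose during sham. P3 does not enter, and no visible analysis compares Visit 10 with a pre-implant score.

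**The concern.** Two features act together. First, the reference for return of pain is one noisy score that had to be low for the subject to be followed at all, and later scores are compared with it repeatedly. Some subjects whose true pain has not moved will therefore meet the definition. Second, the Implant Stage endpoint looks back past the pre-implant state to the period before any active stimulation. Relief carried over from the Trial Stage is then credited to the implant, in full for an unchanged responder and in part after a partial relapse.

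Section 4.3.2 makes return of pain the reason for implanting, and Implant Stage success is a primary endpoint in a single-arm study meant to inform a pivotal trial. With about 18 implanted subjects, each one counted this way moves the success rate by 1/18 = 5.6 percentage points.

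**Working it through.** **The plan's own figures.** The plan expects 45 Trial Stage subjects to yield about 18 implants (18/45 = 40%). The success rates and power inputs behind this are blacked out, so it cannot be reproduced. No chance-qualification rate is visible.

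**Step 1: the written rules, with no assumed variance.** Take P0 = P1 = 8, P2 = 2, two consecutive weekly calls at 4, and P4 = 4.
- Trial Stage success: 8 − 2 = 6 ≥ 2, met.
- Return of pain: 4 − 2 = 2 ≥ 2 and 4 ≥ 4, on both calls, met.
- Implant Stage success: 8 − 4 = 4 ≥ 2, met, although P4 equals the pre-implant score. P4 = 6 would also succeed (8 − 6 = 2), 2 points worse than before implant.

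**Step 2: how often the rules permit this.** With reference 8, P2 runs from 0 to 6, and P3 runs from the larger of 4 and P2 + 2 up to 8. For P2 = 0, 1, …, 6 that gives 5 + 5 + 5 + 4 + 3 + 2 + 1 = 25 pairs. Setting P4 = P3, success needs P3 ≤ 6: 3 + 3 + 3 + 2 + 1 = 12 pairs. So 12 of 25 succeed with no change since the qualifying score. For references 4 and 5 none do (0 of 3 and 0 of 7); at 6, 3 of 12 do. The problem needs a reference of 6 or more. These are counts of score patterns, not probabilities.

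**Step 3: size, by simulation.** Assumptions, none from the documents: baseline mean 7 with between-subject SD 1, no mean sham change, constant true pain after Visit 5, scores rounded to 0–10, lag-1 weekly correlation 0 or 0.4, six monthly calls each with one confirmation a week later, and no implant effect. Share of Trial Stage successes who meet return of pain:

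| Within-subject SD | Relief 3–4 points | Relief 5 points | Relief 6 points |
|---|---|---|---|
| 0.75 | 6–15% | 3–4% | 1% |
| 1 | 13–29% | 6–9% | 1–3% |
| 1.5 | 27–51% | 13–21% | 4–9% |

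Of those who qualify this way, about 68% or more count as Implant Stage successes at Visit 10. Adding a mean sham fall of 0.5 points lowers that minimum to about 63%. For contrast, if pain had truly returned to baseline (mean 7, sham fall 0.5) and the implant did nothing, the same rule would give about 2%, 5% and 13% successes at the three SDs. The gap comes from persisting relief.

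**Step 4: which pre-implant score.** The qualifying call is selected high. If it were the reference, 31–48% of these unchanged subjects at SD 1 would still show a fall of 2 points or more. A fresh score avoids that selection but remains noisy. With independent errors at SD 1, the difference of two scores has SD √2 = 1.41, and a rounded fall of 2 or more has probability about P(Z ≥ 1.5/1.41) = P(Z ≥ 1.06) = 0.14. Correlation between weeks raises this if the fresh score follows soon after the qualifying call.

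**The case against.** - **The confirmation rule is a real safeguard.** A single high call does not qualify anyone: both thresholds must hold again a week later, the score must be at least 4, and the window closes at 6 months. Extra calls are permitted, not scheduled. This stands, and the figures in Step 3 include it. They assume no extra or subject-initiated calls.
- **The percentages depend on where stable pain sits.** Relief of 3–4 points from a baseline of 7 puts true pain at 3–4, next to the floor of 4, where chance crossing is most likely. With relief of 5–6 points the rates fall sharply. This also stands, so no single figure should be quoted.
- **Many subjects may truly relapse.** Section 2.2.3 reports that relief faded after stimulation ended in later-treated subjects. The share of stable responders among the implanted is unknown.
- **The endpoint reference matters more than the call rule.** Agreed. Changing the calls alone would not separate carry-over from implant effect.
- **A reader might infer that no pre-implant BPI3 is collected.** The documents do not establish that: Section 4.5.3.1 names none, but the BPI row in the eligibility block of Table 6 may have carried a mark for Visit Pre-6.
- **This is a pilot.** That supports a reporting change and no more.

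**Conclusion.** The point holds as a weakness in what the Implant Stage endpoint can show. The written rules let a subject qualify for and succeed in the Implant Stage with no change since before implant. Success against Visit 4 or Visit 1 therefore does not separate implant effect from persisting Trial Stage relief. The possibility follows from the text alone. Its frequency does not, because the documents give no within-subject SD, autocorrelation or share of stable responders. Under the stated assumptions, chance qualification of stable responders runs from about 1% to about 51%.

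A reader might go further and conclude that a large part of the implanted group will have qualified by chance, or that the Implant Stage test is falsely positive. Neither is supported. The simulated rates apply only to subjects whose pain never changes, and the null success rate in Section 6.1.2.4 is blacked out, so neither the bias in the trial's success rate nor any effect on the test can be estimated.

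**What to change.** 1. Reconcile Section 4.5.3.1 with Table 6 on whether the BPI is taken at Visit Pre-6. Record BPI3 there as a fresh score that does not decide eligibility.
2. In Section 6.1.2.3, report the Pre-6 to Visit 10 change in BPI3, and the share falling by 2 points or more, beside the existing success rate. Do not use the qualifying call as the pre-implant reference.
3. State in the conclusions that success against Visit 4 or Visit 1 alone does not separate implant effect from persisting Trial Stage relief.
4. Optionally, list each follow-up call (#a–z) with its score and who initiated it. Keep this descriptive: splitting about 18 subjects by call route gives cells too small to compare.

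Individual successes should not be reclassified on the Pre-6 score, since that would rest attribution on one noisy value. Eligibility rules stay with the sponsor and clinicians; none is proposed here.

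The cost is one question at an existing visit and a few lines in Section 6. The reported implant benefit may look less favourable.

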#### **4.5.2.11 Provision for lead replacement during Trial Stage**

During the Trial Stage, it is possible that the Smartpatch Lead may migrate from the intended target location or may become fully dislodged. In the event that the Lead migrates from the intended location significantly (███████████ or if the lead becomes

fully dislodged (i.e. comes out completely), it is possible that the Investigator may elect to place another trial stage lead. This decision will be at the discretion of the Investigator and the Sponsor and should take into account the following considerations 1) the subject’s desire to continue with the therapy and understanding that the same risks of the initial Trial Stage lead placement would apply a second time, 2) the Investigator’s belief that the intended target location is healthy enough to place another lead, and 3) the amount of time remaining in the trial stage.

Subjects who initially required an INR test prior to the first Trial Stage lead placement, will have the test repeated within 48 hours of a second Trial Stage lead placement, as necessary.

If a second Trial Stage lead is placed, subjects will be asked to return to the clinic 48 hours after the lead placement for inspection of the lead exit site. In addition, stimulation therapy will not be turned on for at least one week |███████████. Subjects will then continue with the sham or treatment stage as is appropriate under the protocol.

The risks associated with any additional Trial Stage lead placement procedures are the same as the risks detailed for the initial procedure and are described in Section 8.2 of this protocol. However, subjects will have an additional exposure to this risk.

#### **4.5.3 SPR Implant Stage**

##### **4.5.3.1 Implant Stage Eligibility (Visit Pre-6)**

After a sustained return of pain has been identified, the subject will report to the clinic for Visit Pre-6. First, the study staff will verify that the subject meets all general inclusion and exclusion criteria (with the necessary pain score already having been confirmed at a Trial Stage Follow-up Call). Subjects meeting all general eligibility criteria will be asked if they are interested in participating in the Implant Stage of the study. The Implant Stage Informed Consent Form will be reviewed with the subject to ensure that the risks and benefits of study participation in the Implant Stage are fully understood. The Implant Stage Informed Consent Form may be signed up to 30 days prior to the Implant Stage procedure.

Subjects will then be screened for their cognitive ability to participate in the study and complete the required surveys. The Mini-Mental Status Exam (MMSE) will be administered to determine the subject's continued cognitive ability to participate in the study.

During this visit, the SULCS, and QST testing (optional) will also be administered to subjects for which baseline SULCS and QST data are available.

As a safety precaution to prevent potential excessive bleeding, subjects on warfarin will have blood drawn to confirm an INR of <3.0. If the INR is not below 3.0, subjects will be given the opportunity to have their warfarin dosage adjusted and the INR will be retested up to two additional times. The INR must be collected within 48 hours prior to the Implant Stage procedure. In addition, a pregnancy test will be conducted in females of reproductive potential.

If the subject is determined to be eligible, the Implant Stage procedure (Visit 6) will be scheduled.

##### **4.5.3.2 SPR Implant Stage Procedure (Visit 6)**

Subjects will be asked to comply with any specific preoperative or post-operative instructions (including prescribing of post-surgical pain management analgesics in the week immediately following surgery) or testing that are the standard practice for the implanting surgeon (Investigator). This may require a separate visit to the institution in order to obtain the necessary standard pre-operative tests for clearance to obtain anesthesia.

Prior to the procedure, the IPG will be programmed [REDACTED] [REDACTED]. The settings are based upon the optimal [REDACTED] [REDACTED] that was identified in the SPR Trial Stage.

[figure not shown]
The SPR Implant Stage procedure will be performed in an operating room, [REDACTED]

[REDACTED]

[REDACTED]

[REDACTED]

[REDACTED]

Subjects will be given standard post-operative instructions including restricting physical activity for the first week after the implant procedure and may be prescribed opioid or non-opioid analgesics, as needed, for the management of post-surgical pain during the week immediately following the Implant Stage surgery.

As with the SPR Trial Stage, the SPR Implant Stage procedure may be videotaped for training and educational purposes.

A detailed description of the SPR Implant Stage procedure and IPG programming is provided in the Clinician Manual.

#### **4.5.3.3 1-week Post-Implant/ Turn IPG Stim On (Visit 7)**

One week following the SPR Implant Stage Procedure, subjects will be asked to return to the clinic for a physical inspection of the IPG pocket and Implantable Lead sites and to turn stimulation on.

The Clinician will [REDACTED] program the IPG for the subject. Stimulation parameters will be based [REDACTED] [REDACTED] but will be adjusted as needed. Subjects will be instructed to use the SPR System for a total of 6 hours per day.

The subject will be provided with the IPG Remote and instructed on how to turn the stimulation on/off, how to adjust the intensity [REDACTED] [REDACTED] how to charge the IPG and details on the care and maintenance of the IPG Remote and the other accessories to the SPR Implant System. [REDACTED]

Adverse events will be assessed and a standard post-operative evaluation will be conducted.

